13. Participant Safety:

(This section is required when research involves more than Minimal Risk to participants.)

The study likely poses minimal-to moderate risk since it is not interventional: there is no prescriptive intervention and no requirement for patients or physicians to change medications. The protocol will involve a standard of care medication management approach, albeit informed by drug metabolism and pharmacogenomics information. While polypharmacy patient

populations with co-morbidities are at elevated risk of ADRs, the proposed protocol involves similar or lower risk to participating patients compared to routine clinical practice. Study participants will benefit from standard of care medication management decisions made by clinicians who will be better informed about an individual's pharmacogenomic ability to metabolize the drugs they are taking, and any issues related to drug metabolism that could be affirmed by direct measurement of drug levels (and their metabolites) in blood (in clinical care, outside this study protocol, at the discretion of the provider). In short, the protocol is likely to enhance the safety of research subjects relative to patients receiving standard of care in a primary care setting without the information this study will provide. In this vein it should be noted that the FDA has a current posture of not regulating physician facing clinical decision support tools (24). However, the FDA has issued nonbinding guidance (25) for Software as a Medical Device (SaMD) that recommends design control and clinical evaluation standards, including the use of third-party certifications, for SaMD. While the ActX CDS and the pharmacogenomic dashboards being used in this protocol are not subject to FDA regulation under the SaMD framework (like most electronic medical record readouts), the ActX CDS platform has received [certification](#) from rigorous third party (ONC-Authorized Certification Bodies) evaluation. These established standards in the health informatics industry establish low tolerances for computational or design flaws in software that can render erroneous information for clinical decision making that poses risks to patients.

There are inherent risks of morbidity and mortality associated with taking, changing, or discontinuing medications in whatever standards-of-care are applicable to an individual's case. These risks are routinely weighted by the physician in the practice of medicine, and no actions beyond the exercise of physician judgments are prescribed under this protocol. IPGx will forward specific recommendations to the referring physician who in turn will make changes to the regimen, as desired. It is expected that changes made to mitigate a polypharmacy burden would reduce risk of ADRs. We do not expect these risks to differ from those inherent to the medication of choice and adjustments thereto during standard medical care.

It should be noted that standard of care for changing most medications is simply trial and error (22), with a few exceptions warranting pharmacogenomic testing though consensus medical guidelines for actions based on results of pharmacogenomic exist and are endorsed by [Association for Molecular Pathology](#), [American Society for Clinical Pharmacology and Therapeutics](#), and the [American Society of Health-System Pharmacists](#). The working principle for this program is that the risks of being a polypharmacy patient without medication management care are greater than the risks of trying to ameliorate that burden with pharmacogenetic and drug level testing to inform medication management. In many respects that study can be viewed as a quality improvement project for participating clinics. For these reasons, the proposed study is one of minimal to no risk.

Any risk will be minimized by exercising the same level of clinical decision prudence that any active medical practice would take during clinical care delivery to monitor a patient's safety and condition. Licensed practitioners would be taking care for patients in compliance with standards of care, state licensure regulations and any rules of safety practices associated with the United States, the State of Texas, and Texas A&M University. Clinicians would make all final clinical decisions, in accordance with standard of care practices for the medical conditions in each clinical case.

It is expected that study participants remain engaged with the primary care clinic from where they were referred. Since the period of data collection is 180 days and the recommendation calls for periodic re-evaluation of the enrollee, if concerns arise the referring clinician would help

IRB NUMBER: STUDY2024-0724
IRB APPROVAL DATE: 9/18/2024

address the need to monitor safety. Lab data will be reviewed as it becomes available. We will establish a safety monitoring board constituted by team members to oversee and report any adverse events issues or episodes to the IRB. Because medication management is expected to align with standard of care and within normal parameters of physician judgment, the risk of adverse outcomes is minimal relative to a care plan that omits a medication management element and the polypharmacy and pharmacogenomics information that will be made available to the care team.

Data Safety Monitoring Plan.

Clinical study staff and investigators, under the supervision of the PI will review all data on an ongoing basis for data completeness and accuracy as well as protocol compliance. All data will be appended to the eCW medical record and reconciled by [name] (or another ambulatory pharmacist in the clinic) when each subject first presents to the IPGx. Drs. [name], [name], and [name] will review the safety and progress of the study quarterly, after medication changes occur in at least 5 subjects. Study reports, including patient recruitment, retention/attrition, and AEs, will be produced following each of the quarterly reviews. Study reports will be compiled for each subject at the close-out of this pilot study, with a study report for each case appended to the ActX CDS for record keeping.

Items to be in the closeout report and reviewed by the PI include:

- Interim/cumulative data for evidence of any study-related adverse events and serious adverse events;
- Summary of data quality, completeness, and timeliness;
- Adequacy of compliance with goals for recruitment and retention, including those related to the participation of women and minorities;
- Adherence to the protocol;
- Factors that might affect the study outcome or compromise the confidentiality of the trial data (such as protocol violations); and,
- Factors external to the study such as scientific or therapeutic developments that may impact participant safety or the ethics of the study.

AEs will be noted in the eCW categorized according to the likelihood that they are related to the study. Specifically, they will be labeled unrelated, related, probably related, or possibly related to the study intervention. AEs will be labeled according to severity, which is based on their impact on the patient. An AE will be termed “mild” if it does not have a major impact on the patient, “moderate” if it causes the patient some minor inconvenience, and “severe” if it causes a substantial disruption to the patient’s well-being. In the final study report, the PI will attest that they have reviewed all AE reports.

A serious adverse event (SAE) is any adverse event that results in one or more of the following:

- Death
- A life-threatening event
- Inpatient hospitalization or prolongation of existing hospitalization
- A persistent or significant disability/incapacity
- A congenital anomaly or birth defect

Any SAEs will be documented and reported to the TAMU IRB in accordance with HRP-029 (5 business days or less).

The PI or his designee will codify each review with their actionable recommendations to IPGx as to whether the study should continue without change, be modified, or be terminated.

Recommendations regarding modification of study could include:

- Changes of the study protocol raised by the review of the safety data;
- Suspension or early termination of the study because of serious concerns about subjects' safety, inadequate performance, or rate of enrollment;
- Corrective actions regarding a study center whose performance appears unsatisfactory or appears to raise questions regarding the conduct of the study.

Immediate Action Report: The clinical Investigators will notify the PI and TAMU HRPP/IRB of any observations of a serious and immediate nature or recommendations to discontinue all or part of the study. In addition to verbal communications, recommendations to discontinue or substantially modify the design or conduct of a study must be conveyed to the PI and the TAMU HRPP/IRB in writing by e-mail, fax, or courier within 5 business days of occurrence.

The study period is limited (one visit and 12 months of chart analysis- 6 months before the index date and 6 months after the index date), the number of subjects is small (n=50), and the risks to subjects are of low likelihood and low magnitude of harm, so stopping for futility is not justified.

14. Withdrawal of Participants:

An individual can be suspended or removed from the research protocol due to non-compliance with visits. Issues such as pregnancy, admission to hospice, death, will be evaluated by clinical staff in consultation with the principal investigator. Adverse Drug Responses (ADRs) as defined by Aronson: *“arise when a compound (e.g. a drug or metabolite, a contaminant or adulterant) is distributed in the same place as a body tissue (e.g. a receptor, enzyme, or ion channel), and the encounter results in an adverse effect (a physiological or pathological change), which results in a clinically appreciable adverse reaction.”* (26). For clarity, ADRs will not necessarily be a reason for removal of a subject from the study. An orderly termination procedure would include written notice and or documented phone call between the subject if appropriate, and a member of the care team. Enrollees will be given a two-week notice. The only safety reason for termination is the determination by the medical staff the patient's condition necessitates discontinuation of participation in the study. An example would be a determination by the physician that continued participation in the study would be deleterious to the enrollees' health. If a patient withdraws from the research, they will still be able to continue to be a patient at the IPGx.

15. Risks to Participants:

Risks involved:

- Other discomfort, hazards, or inconveniences, taking into consideration physical psychological, social legal, and economic risk of possible privacy breach of WGS data.
ML

An erroneous test result could result in an unnecessary, or even harmful medication change
PL, ML

- Phlebotomy along with its associated risks ranging from ecchymoses, hematoma, nerve injury, infection. PL

IRB NUMBER: STUDY2024-0724
IRB APPROVAL DATE: 9/18/2024

Key

Probability P | Magnitude M | Duration D | Short S | Low L | Moderate M Extensive E

The use of the PGx dashboard of the PGx test results does not alter the magnitude of risks to subjects whose medications are changed from one standard of care medication to another standard of care medication. These choices are made by physicians, within their professional discretion and statutory scope of practice, and regrettably, it is common for medications to be harmful because of the unknown genetics of the patient or unrevealed drug interactions. These choices are routinely made by primary care physicians (and specialists) without the benefit of understanding whether a patient may be experiencing adverse drug reactions and understanding whether those reactions may be a result of drug-drug interactions to drug-gene interactions. Put another way, the menu of choices of medications is not altered under the Protocol or by virtue of Pilot Study WGS Extension participation, only that the physician is more informed.

The likelihood of new risk is slightly increased in that test results could be erroneous or improperly rendered by the ActX CDS. In such a case, the physician may choose a new standard of care medication while *misinformed* about the genotype of a patient. This is no worse than choosing a new standard of care medication while *uninformed* about the genotype of a patient. The likelihood of such errors is inherent in all CLIA tests that are used pervasively in the practice of medicine, and the probability and magnitude of risk to the patient is minuscule. One of the two principle of beneficence in the Belmont Report is to “maximize the possible benefit and minimize possible harms.” In the present case, the benefits of informing medication management far outweigh the inherent risks of making suboptimally informed medication management decisions (or doing nothing) when the medications the patient is currently taking are suspected of currently inflicting harm. Subjectively, the likelihood and magnitude of harm to subjects are low while the potential benefits are highly probable.

Test results from CAP/CLIA laboratories for high complexity LDTs that have undergone proficiency testing have low probability of being erroneous. Additionally, the ActX platform classifies the predicted severity/magnitude of ADR for specific drug-gene variant pairs of known clinical significance and provides customizable alerts for such pairs. If patient experience with a medication is incongruent with predicted phenotypes (e.g. tolerance and response to a change in medication), medication levels can be measured under this protocol (with no cost to patient or insurance) to confirm the medication is within known therapeutic windows.

17. Potential Benefits to Participants:

The study is designed in alignment with the principles of *Standards in the Conduct of Registry Studies for Patient-Centered Outcomes Research – Report to PCORI* [11]. A description of the scope of the polypharmacy problem is described in more detail in Sections 3: Objectives, 4: Background, 9: Outcome measures, 13: Participant Safety.

Additionally, we seek to understand how and when polypharmacy begins the cascade of ADRs such as ED visits, falls, or expression of another comorbidity. Our expectation is that a patient will experience reduced polypharmacy burden, and that participation in a medication management program with pharmacogenomic and informed drug dose titration (when warranted), will reduce ADRs that are common and frequent in these populations. We also expect that participation will improve adherence.

IRB NUMBER: STUDY2024-0724
IRB APPROVAL DATE: 9/18/2024

The clinical burden of highly prevalent anticholinergic medications can be quantitatively monitored such that refined use of this class of drugs has substantial potential to inform and impact this major contributor to polypharmacy burden.

Benefits of the study for the healthcare and scientific communities

The potential benefit and reason for requesting this study is to develop a polypharmacy solution utilizing electronic clinical decision support, pharmacogenomic studies, and blood drug levels (derived from urine drug levels in this study). We might understand the impact of comorbidities such as depression or cognitive problems due to non-compliance. These phenomena are major drivers of high healthcare utilization, with genetic and social determinants. This care team strategy enables the collection of data underlying these factors. It can help inform clinical decision making (medication adjustments) in a manner that improves quality of life (reduced side effects), and clinical outcomes for patients (improved efficacy).

As the enrolled population and our database grow, we might identify novel genotypes for drug metabolism that inform precision dosing and improve risk management through medication management programs. Our informed consent form, collaborative structure, and contracts will thoughtfully account for the best way to allow for compliant and deidentified sharing of the data collected under this protocol with the clinical and scientific community, including but not limited to peer-reviewed publication.

18. Vulnerable Populations:

Not eligible.

19. Sharing of Results with Participants:

The results of the IPGx's evaluation and management, such as lab data, pharmacogenomics results, and drug blood levels (inferred from urine drug levels in this study), will be shared with the referring physician in Texas A&M Family Care Clinic and patients as soon as it is practical during care, referred back to the referring physician with a report to explain medication management recommendations. Results may be shared, utilizing all means of communication commonly available to physicians in the practice of medicine. For example, at the time of visit or by phone. The rationale for this is that clinical decisions will be made regarding medication management, and the patient will be an engaged participant in that process. Results in the form of a precision medication management dashboard report summarizing germane information about drug concentrations and relevant CYP variants, will be shared with the ordering physician and the referring physician/primary care physician in written form. Results of WGS are research use only and will not be clinically actionable and not shared with healthcare providers or research participants. Incidental findings will not be shared with participants under this protocol.

20. Setting:

Texas A&M University. Research participants will be recruited from the patients referred to the IPGx clinic from their primary care physician for polypharmacy problem consultation. The outpatient IPGx clinical site will be a clinic owned and managed by Texas A&M Health. Participants will be recruited from Texas A&M primary care clinics. Collaboration with the primary care

IRB NUMBER: STUDY2024-0724
IRB APPROVAL DATE: 9/18/2024

component would involve patients who meet inclusion criteria prescribed by this protocol. In some instances, as requested by the referring physician, IPGx clinicians will make medication change recommendations, and keep the referring clinic apprised of these recommendations. If a patient wishes to be seen at the IPGx but does not meet inclusion criteria, all recommendations will be directly reported to the referring primary care clinic for review and determination. The research will be performed at the clinic site designated by Texas A&M, but some bioanalytic sample analysis will occur offsite.

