Our primary aim is to evaluate polypharmacy-associated adverse drug reactions (ADR) in a pilot study of at-risk patients using state-of-the-art pharmacogenomic technology and to use this information to make recommendations for optimization of pharmacotherapy regimens. The data from the pilot cohort will be used to optimize and integrate a customized electronic decision support (ActX) dashboard to identify medications that should be modified, replaced, or discontinued. A secondary objective of the pilot study is to evaluate the capacity/saturation of CYP P450 enzymatic pathways in polypharmacy patients. A third objective is to determine the feasibility of the planned informatics workflows between the CLIA lab, the Electronic Medical Record (EMR), and the Family Medicine Practice, including Whole Genome Sequencing (WGS). There is no prospective comparison group because this is a pilot study for a registry. WGS sequencing data will be for research use only, will not be used for clinical decision making, and will not be reported back to prescribing practitioners - these data will only be used to assess the feasibility of use for that type of genetic test data in the IPGx informatics workflow.

This protocol adds an extra research component to the PILOT protocol: WGS for research use only (RUO). This data will not be stored in the medical record or made available to physicians for clinical decision support. No additional office visits or samples will be required during scheduled healthcare visits to Family Medicine or IPGx.

Performing WGS is essential for the following reasons:

- 1) To obtain real data for optimizing the complex data pipelines and workflows involved in WGS.
- 2) To enable the identification of novel variants that genotyping cannot accomplish.
- 3) To initiate concurrence analysis of WGS against genotyping for known variants in our PGx genotyping test.
- 4) To demonstrate and validate the use of our digital data governance tools for stakeholders.

Collectively, these essential functions are critical capabilities needed to successfully compete for federal grant funding.

4. Background:

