- Emergency department visits
- Hospital admissions
- Serum/plasma drug concentrations
- Pharmacogenomic genotype with corresponding ADR phenotype
- Drug-drug interactions, drug-gene interactions, drug-drug-gene interactions

10. Procedures Involved:

Patients will be referred to the Texas A&M Interprofessional Pharmacogenomics Clinic (IPGx) by their primary care physicians to evaluate polypharmacy status, genotyping, pharmacokinetic/pharmacodynamic (PK/PD) assessment, and monitoring of potential for ADR.

An assessment at the IPGx will start with the pharmacist or physician doing a pharmacologic consultation to evaluate medications or other drugs currently being used by the patient and to identify any potential issues related to toxicity, drug interactions, or side effects that might be relevant to the clinical presentation. A physician or ambulatory pharmacist in the IPGx clinic or Family Care Clinic will obtain a complete medical history, physical examination, and validate the patient's current concomitant medication list at the IPGx during the office visit. Other clinical team members may include house staff or medical students, a clinical/research coordinator, and a nurse. Patients eligible for inclusion in the research study will be offered enrollment. Patients who choose not to participate in the study are still eligible to receive care, without prejudice. After providing detailed educational instruction and informed consent, including the risks and

IRB NUMBER: STUDY2024-0724
IRB APPROVAL DATE: 9/18/2024

benefits of the study, patient medical information would be input into the ActX CDS, which functions as a computable EHR. The **attached informed consent** obtains permission from every individual to use their clinical, genetic, and lab data.

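### Section 14 allows removal from the research for missed visits, although ED visits, admissions and documented ADRs are read from the chart, so obtainable outcome data could be lost

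*Protocol*

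**What the plan says.** Section 14 (Withdrawal of Participants) states: "An individual can be suspended or removed from the research protocol due to non-compliance with visits". It continues: "Issues such as pregnancy, admission to hospice, death, will be evaluated by clinical staff in consultation with the principal investigator". It adds that an ADR need not lead to removal, and that enrollees get two weeks' notice.

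Section 13, in the data safety monitoring plan, describes the design as "one visit and 12 months of chart analysis", with half a year of records read on either side of the index date, in 50 subjects. The objectives text says of the added sequencing component: "No additional office visits or samples will be required during scheduled healthcare visits to Family Medicine or IPGx".

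Section 9 lists "Emergency department visits" and "Hospital admissions" as outcomes, with ADRs on the Naranjo scale and drug concentrations. Section 10 names the sources: ED or urgent-care notes, hospital visits, and ADRs that are either self-reported or documented. Section 8 allows record access for 180 days from enrolment and none afterwards. Section 11 describes the research activities that begin at consent as data collection only.

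**The concern.** The removal rule does not fit the design. Attendance is made a condition of staying in the research, yet several listed outcomes do not depend on attendance. A person who stops coming to the clinic can still have ED visits, admissions and documented ADRs read from the chart until day 180.

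At stake is an avoidable selection. If the reason for missing a visit is connected with illness, removal is connected with the outcomes, and event frequencies in the six months after the index date would describe a selected group. Section 17 expects ADRs to fall with participation, so a downward bias would resemble the expected benefit. This is a rule of conduct: a later analysis plan cannot recover charts that were never read within the access window.

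**Working it through.** The protocol gives no event rate, dropout rate, effect size or power, and n = 50 has no derivation. There is no figure to reproduce. The check is a comparison of the text, followed by an illustration on assumed rates.

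**1. The text side by side**

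- *Which visits count?* Section 13 names one visit. Section 8 allows further IPGx appointments if the primary care physician refers the patient back. Section 10 says patients are seen after the final report, and Section 13 mentions periodic re-evaluation. None has a date or a required number, so non-compliance has no defined standard.
- *Which outcomes need a visit?* ED visits, admissions and documented ADRs do not. Self-reported ADRs need contact and drug concentrations need a sample.
- *What does removal end?* If the research activity is data collection (Section 11), removal from the research ends collection on its natural reading. Section 14 does not say so outright. It also does not say that chart follow-up continues.
- *Can the loss be repaired?* Not after day 180 (Section 8).

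**2. Illustration of size**

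Let p be the true 180-day risk among all enrolled, d the share removed, RR the risk in those removed relative to those retained, and r the risk in those retained. All values are assumptions. Since p = (1 − d)·r + d·RR·r,

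r = p / (1 − d + d·RR), and the relative bias is 1 / (1 − d + d·RR) − 1.

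| p | d | RR | r | Bias, points | Relative bias |
|---|---|---|---|---|---|
| 10% | 5% | 2 | 0.10/1.05 = 9.5% | −0.5 | −4.8% |
| 20% | 10% | 2 | 0.20/1.10 = 18.2% | −1.8 | −9.1% |
| 30% | 20% | 3 | 0.30/1.40 = 21.4% | −8.6 | −28.6% |
| any | any | 1 | p | 0 | 0 |
| 30% | 20% | 0.67 | 0.30/0.934 = 32.1% | +2.1 | +7.1% |

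Over p = 10–30%, d = 5–20% and RR = 2–3, the bias runs from −0.5 to −8.6 points. With RR = 0.67 it runs from +0.2 to +2.1 points.

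**3. What the formula leaves out**

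It drops every event of a removed participant, including those before removal. Take 50 enrolled, 10 removed with a 40% risk and 40 retained with a 15% risk. The true risk is (10×0.40 + 40×0.15)/50 = 10/50 = 20%.

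- Removed participants dropped entirely: 6/40 = 15%.
- All 4 of their admissions before removal, and kept: 10/50 = 20%, no bias.
- All 4 after removal, charts not read, but the 10 kept in the denominator: 6/50 = 12%.

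Timing and handling therefore matter as much as the assumed rates.

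**4. Scale**

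The 95% half-width at n = 50 and p = 20% is 1.96×√(0.20×0.80/50) = 0.111, about 11 points. The illustrated bias is smaller than that, but a larger sample would not remove it.

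**The case against.** The strongest defence has five parts.

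- *Removal is discretionary.* Section 14 says a person can be removed, not that they will be, and it does not state that chart reading stops. This stands as a limit on how often the problem would arise. It does not settle what happens to the data when someone is removed.
- *Visits have some function.* Self-reported ADRs, follow-up samples and the contact after the report depend on attendance. This stands, and it is why the point is confined to outcomes read from the chart.
- *Events that cause missed visits may precede removal.* A patient admitted to hospital and then removed has already had the event. This stands: only events after removal are at risk, provided earlier data are kept, which the protocol does not say.
- *Handling of removed participants may be set out in an SAP that was not available.* This stands for the analysis, but not for data that were never collected.
- *This is an uncontrolled pilot.* Section 12 specifies no before-and-after test, and the expected fall in ADRs appears under potential benefits. This lowers the stakes, although event frequencies are still listed outcomes.

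A reader might go further and infer that the sickest patients will drop out and that events are therefore understated. The protocol has no attendance or severity data to show it. Section 4 links polypharmacy with hospitalisation and loss of function, which makes such a link plausible but does not establish it.

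A reader might also infer that patients who die or enter hospice vanish from the data. Section 14 says only that these cases will be evaluated, and Section 13 requires deaths and inpatient hospitalisations to be documented and reported as serious adverse events. Nor does the protocol say that the six months before the index date are complete for everyone.

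**Conclusion.** The inconsistency is established: a visit-compliance ground for removal, with no defined visits, sits in a study whose ED, admission and documented-ADR outcomes need no visit. It follows, on the natural reading of removal from data-collection research, that obtainable data after removal would be lost and could not be recovered after day 180.

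The bias is conditional. It arises only if people are in fact removed and missed visits are related to the outcomes, or if removed participants stay in the denominator with unread charts. A downward direction is more likely than not, but is not fixed by the protocol. On the assumed ranges the shift runs from about +2 to −9 percentage points when removed participants are dropped entirely, and is nil at equal risk or if all their events precede removal and are kept. The point is strongest for ED visits and admissions and weaker for ADRs, some of which are self-reported.

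**What to change.** In Section 14:

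- State that missed visits end only visit-based procedures (samples and self-report).
- State that chart follow-up of ED visits, admissions and documented ADRs continues to day 180 for all enrolled, unless consent to data use is withdrawn.
- Keep all data collected before any removal.
- Record death and hospice admission as dated events.
- Report removals with their reasons.

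Clinical grounds for stopping participation are left as they are.

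The cost is a few sentences, chart extraction for a few non-attending participants, and a check that the consent form, which was not available, covers continued reading of the record. If all charts are read to day 180, the selection in these outcomes due to this rule disappears.
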